11.2 Source Documents

Source documents are defined as the results of original observations and activities of a clinical investigation. Source documents will include, but are not limited to, progress notes and screening logs. All source documents pertaining to this study will be maintained by the investigators and made available for inspection by authorized persons. The original signed informed consent form for each participating subject shall be filed with records kept by the investigators and a copy given to the subject.

11.3 File Management at the Study Site

Protocol No: PRG-NY-14-008

It is the responsibility of the investigator to ensure that the study center file is maintained in accordance with Section 8 of the International Conference on Harmonization (ICH) Guideline for Good Clinical Practices (GCP).

11.4 Records Retention at the Study Site

FDA regulations require all investigators participating in clinical drug studies to maintain detailed clinical data for one of the following periods:

- a) A period of at least two years following the date on which a New Drug Application is approved by the FDA;
- b) A period of two years after the sponsor notifies the investigator that no further application is to be filed with the FDA.

The investigator must not dispose of any records relevant to this study without either (1) written permission from the sponsor or (2) providing an opportunity for the sponsor to collect such records. The investigator shall take responsibility for maintaining adequate and accurate electronic or hard copy source documents of all observations and data generated during this study, including any data clarification forms (DCFs) received from [REDACTED]. Such documentation is subject to inspection by the sponsor and the FDA.

12. QUALITY CONTROL AND QUALITY ASSURANCE

12.1 Monitoring

The sponsor has ethical, legal and scientific obligations to carefully follow this study in a detailed and orderly manner in accordance with established research principles and FDA regulations. All medical records (source documents) of the subjects participating in this study must be presented for review and verification of eCRFs. Monitors must be given direct access to either original or certified copies of the medical records.

12.2 Auditing

The sponsor (or representative) may conduct audits at the study center(s). Audits will include, but are not be limited to, drug supply, presence of required documents, the informed consent process, and comparison of case report forms with source documents. The investigator agrees to participate with audits conducted at a reasonable time in a reasonable manner.

Regulatory authorities worldwide may also audit the investigator during or after the study. The investigator should contact the sponsor immediately if notified of such an audit, and

Protocol No: PRG-NY-14-008

must fully cooperate with the audits conducted at a reasonable time in a reasonable manner.

13. ETHICS AND RESPONSIBILITY

This study must be conducted in compliance with the protocol, Declaration of Helsinki, the United States Food and Drug Administration (FDA) regulations, any other countries regulations, and ICH GCP Guidelines

1 LIST OF ABBREVIATIONS AND DEFINITIONS OF TERMS

Table 1: Abbreviations and Definitions of Terms

AE(s)	Adverse event(s)
ANOVA	Analysis of variance
ATC	Anatomical therapeutic chemical
BMI	Body mass index
CI	Confidence interval
CIP	Clinical investigation plan
cm	Centimeters
CMH	Cochran-Mantel-Haenszel
CSR	Clinical Study Report
eCRF	Electronic case report form
ENT	Ear, nose, and throat
H ₀	Null hypothesis
H ₁	Alternative hypothesis
HSV	Herpes simplex virus
ICF	Informed consent form
IRAE	Immediately reportable adverse events
ITT	Intent-to-Treat
kg	Kilogram
Max	Maximum
MedDRA	Medical Dictionary for Regulatory Activities
Min	Minimum
mITT	Modified Intent-to-Treat
N	Number of subjects
PP	Per-Protocol
PT	Preferred term
RHL	Recurrent herpes labialis
SAE	Serious adverse event
SAP	Statistical analysis plan
SAS®	Statistical analysis software
SOC	System organ class
SD	Standard Deviation
SOP	Standard operating procedures
TCR	Theorem Clinical Research
TEAE	Treatment-emergent adverse event
WHO	World Health Organization
UNIX	UNiplexed Information and Computing Service

2 INTRODUCTION

[REDACTED]

[REDACTED]

[REDACTED]

An aborted episode is defined as a typical, recurrence-associated localized, site-specific

[REDACTED]

[REDACTED] Perrigo has developed a generic formulation of

Acyclovir Cream, 5%.

[REDACTED]

[REDACTED]

[REDACTED]

3 STUDY OBJECTIVES

The objectives of this study are:

1. To compare the safety and efficacy profile of Perrigo's Acyclovir Cream, 5% to Valeant's Zovirax[®] Cream 5%.
2. To demonstrate the bioequivalence of Perrigo's Acyclovir Cream 5% (test product) to Valeant's Zovirax[®] Cream 5% (reference product).
3. To demonstrate the superiority of efficacy of Perrigo's Acyclovir Cream, 5% and Valeant's Zovirax[®] Cream 5% over Perrigo's Vehicle of Acyclovir Cream, 5%.

4 STUDY DESIGN

4.1 General Design

This is a multi-center, double-blind, randomized, vehicle-controlled, parallel-group bioequivalence study, conducted in subjects with recurrent herpes simplex labialis.

The subjects will be randomized to one of the following treatment groups

- 1) Acyclovir Cream, 5% - Perrigo
- 2) Zovirax[®] (Acyclovir) Cream 5% - Valeant Pharmaceuticals
- 3) Vehicle of Acyclovir Cream, 5% - Perrigo

The objective of the study is to demonstrate bioequivalence of Perrigo's Acyclovir Cream, 5% and Valeant's Zovirax[®] (Acyclovir) Cream, 5% based on the primary clinical endpoint of time-to-complete healing of lesions. As a parameter for determining adequate study sensitivity, statistical superiority ($p < 0.05$) of active formulations over vehicle control needs to be demonstrated with regard to the primary endpoint.

Subjects will be immunocompetent males and females, ≥ 12 years of age, with a clinical diagnosis of non-life-threatening recurrent herpes simplex labialis.

When a subject meets the inclusion/exclusion criteria, the subject will be randomized to one of the above mentioned study treatment arms. Subjects will apply the study medication at 5 times a day for 4 days.

[REDACTED]

[REDACTED] At this visit, the investigator will identify a target area and mark it in the source document.

Subjects will maintain a diary in which they will record each time and date of study medication application in addition to recording any adverse events experienced or medication used.

Visits to the study site are scheduled at screening visit (Visit 1), treatment visits on Days 2 (Visit 3), 3 (Visit 4) and 4 (Visit 5) and follow-up visits on Days 5 (Visit 6), 6 (Visit 7), 7 (Visit 8), 8 (Visit 9), 10 (Visit 10), 12 (Visit 11), 14 (Visit 12) and 21 (Visit 13).

[REDACTED]

[REDACTED]

[REDACTED]

If healing occurs in-between scheduled study days, the subject should return to the clinic

[REDACTED]

4.2 Discussion of Study Design

This study is designed to demonstrate the bioequivalence of Perrigo's Acyclovir Cream, 5% to Valeant's Zovirax[®] Cream 5% and will also demonstrate the superiority of efficacy of Perrigo's Acyclovir Cream, 5% and Valeant's Zovirax[®] Cream 5% over Perrigo's Vehicle of Acyclovir Cream, 5%. This study has the following design characteristics:

- Randomized: This is done in order to eliminate the allocation bias and balancing both known and unknown prognostic factors, in the assignment of treatments.
- Vehicle control (Placebo): This study involves a Vehicle group that will be used to demonstrate the superiority of the test and reference formulations.
- Bioequivalence: To establish bioequivalence between Perrigo's Acyclovir Cream, 5% (test) and Valeant's Zovirax[®] Cream 5% (reference), the 90% confidence interval of the test/reference ratio for the primary endpoint, time-to lesion healing, must be contained within [0.80, 1.25]
- Superiority: As per the FDA guidelines, if bioequivalence is demonstrated for test and reference formulations, this will only be accepted if the study had adequate sensitivity to detect true differences between formulations if they existed. Hence, this study is designed to demonstrate the superiority of Perrigo's Acyclovir Cream, 5% and Valeant's Zovirax[®] Cream 5% over Perrigo UK FINCO's Vehicle of Acyclovir Cream, 5%.

4.3 Method of Assignment of Subjects to Treatment Groups

Eligible subjects will be randomized to one of the following treatment groups in a 1:1:1 allocation ratio:

- Test Formulation: Acyclovir Cream, 5% - Perrigo
- Reference Formulation: Zovirax[®] Cream 5% - Valeant Pharmaceuticals
- Vehicle: Vehicle of Acyclovir Cream, 5% - Perrigo

Randomization will be performed according to a computer-generated randomization scheme where the treatment group designation has been assigned to the subject number. The treatment designation will remain blinded until the final database is locked. An

independent third party will hold the randomization code throughout the study. The randomization scheme will be a block randomization.

4.4 Blinding

Being a double-blind study, the subject, investigator, staff at the study site, study monitors, and data analysis/management personnel are blinded to treatment assignments. Study medication is blinded, labeled and packaged, according to the randomization code, so that neither the subject nor the investigator can identify the treatment. Each subject's treatment unit will consist of one kit box containing [REDACTED] study medication. One tube will be distributed to the subject and the second will remain at the site as a back-up sample to be distributed if necessary only. The tear-off portion of the kit label contains the identity of the study medication in the kit. In the event of an emergency, the specific subject treatment may be identified by removing the overlay of the blinded label, which should be attached to the study medication dispensing log; however, every effort should be made to maintain the blind. The investigator must not scratch off the occluding layer of the label unless absolutely necessary to provide medical treatment to a subject in an emergency situation and should seek prior authorization by the sponsor or designee when possible. If the occluded portion of the label is removed, each involved subject(s) will be discontinued from the study and the reason for breaking the blind will be clearly documented in the source documentation and electronic case report form (eCRF). The sponsor must be notified immediately about any unblinding situation.

Unblinding of individual subject treatment assignments will occur following database hard lock by the Theorem Clinical Research Biometrics department.

4.5 Determination of Sample Size

[REDACTED]

[REDACTED]

5 CHANGES IN THE CONDUCT OF THE STUDY OR PLANNED ANALYSES

5.1 Changes in the Conduct of the Study

[REDACTED]

5.2 Changes from the Analyses Planned in the Protocol/CIP

[REDACTED]

[REDACTED]

Table 2: Assessments Conducted at each Scheduled Visit (cont.)

| [REDACTED] |
|------------|------------|------------|------------|------------|------------|------------|------------|
| [REDACTED] |
| [REDACTED] | | | | | | [REDACTED] | [REDACTED] |
| [REDACTED] |
| [REDACTED] |
| [REDACTED] |
| [REDACTED] | [REDACTED] | | | | | | |
| [REDACTED] |
| [REDACTED] |
| [REDACTED] | [REDACTED] | | | | | | |
| [REDACTED] | [REDACTED] | [REDACTED] | [REDACTED] | [REDACTED] | [REDACTED] | | |

[REDACTED]

6.2 Time Point Algorithms

6.2.1 Relative Day

[REDACTED]

[REDACTED]

6.2.2 Length of Time-to-Event Parameters

[REDACTED]

[REDACTED]

Please note, the hours maybe converted to days (24 hours in 1 day),

6.2.3 Windows

The clinic visits will be scheduled as per the following visit window:

If a subject arrives on an unscheduled visit, then the same assessment procedures will be performed as a scheduled follow-up visit.

Data will be summarized as per scheduled study visits only. No windowing of visits will be performed for data analysis.

Table 3: Clinic Visit Window

Visit	Scheduled Study Day	Protocol Visit Window
Visit 2 (Day 1)	The date of initial application	Day 1
Visit 3 (Day 2)	Day 2 (within 24 hours of treatment initiation)	Day 2 (within 24 hours of treatment initiation)
Visit 4 (Day 3)	Day 3	Day 3
Visit 5 (Day 4)	Day 4	Day 4
Visit 6 (Day 5)	Day 5	Day 5
Visit 7 (Day 6)	Day 6	Day 6
Visit 8 (Day 7)	Day 7	Day 7
Visit 9 (Day 8)	Day 8	Day 8
Visit 10 (Day 10)	Day 10	Day 10
Visit 11 (Day 12)	Day 12	Day 12
Visit 12 (Day 14)	Day 14	Day 13 - 15
Visit 13 (Day 21)	Day 21	Day 19 - 23

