3.3 Study Design

Screening Visit:

During Visit 1, once the subject meets inclusion-exclusion criteria, they will be randomized and given the study medication. [REDACTED]

Protocol No: PRG-NY-14-008

[REDACTED]

[REDACTED]

[REDACTED]

Treatment Visits:

Subjects will come in for Day 1 (Visit 2) [REDACTED]. At this visit, they will be questioned regarding onset of the episode. The investigator will identify a target area and mark it in the source document.

Clinic visits will take place on Days 2 (Visit 3), 3 (Visit 4) and 4 (Visit 5).

All subjects must be treated with the study medication for 4 days even if the lesion has healed before treatment ends.

Follow-up visits:

The subjects will return their study medication on Day 5 (Visit 6).

Subsequent follow up visits will take place on:

- Days 6 (Visit 7), 7 (Visit 8), 8 (Visit 9), 10 (Visit 10) and 12 (Visit 11).
- Day 14 (Visit 12) will have a window +/- 1 day (i.e. Day 13-15).
- Day 21 (Visit 13) will have a window of +/- 2 days (i.e. Day 19-23).

[REDACTED]

Note:

If the subject's lesion has healed prior to Day 5 (Visit 6), the subject will continue to apply the study medication as proposed for 4 days, and return for all study Visits up to Day 5 (Visit 6), which will be their End of Study Visit.

Protocol No: PRG-NY-14-008

If the lesion is healed after Day 5 (Visit 6) but before Day 21 (Visit 13), the subject will return for their End of Study visit as directed by protocol upon healing and will not have to continue coming to the clinic for the remaining study visits.

[REDACTED]

[REDACTED]

If a subject arrives to the clinic for an unscheduled visit, the subject will go through the same procedures as a scheduled follow-up day. If the subject has not healed by this unscheduled visit, the subject will return to the clinic for the subsequent previously planned follow-up visits.

The use of the study medication should be discontinued after Day 4; however the investigator will continue to monitor the lesion until Day 21 if not healed by then.

[REDACTED]

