5.7.2 Application Site Reaction Assessment

Protocol No: PRG-NY-14-008

At Day 1 (Visit 2) and at each subsequent visit, application site reactions such as dry lips, desquamation, dryness of skin, cracked lips, burning skin, pruritus, flakiness of skin and stinging on the skin (if any) will be recorded.

Site Reaction	DESCRIPTION
Dry Lips	
Desquamation	
Dryness of Skin	
Cracked Lips	
Burning skin	
Pruritus	
Flakiness of Skin	
Stinging of the skin	

SCORE	ASSESSMENT	DESCRIPTION
0	None	
1	Mild	
2	Moderate	
3	Severe	

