7. ADVERSE REACTIONS

The potential adverse reactions of generic Acyclovir Cream, 5% are anticipated to be similar to those observed in Zovirax® Cream 5%. Adverse reactions related to treatment with Zovirax® Cream 5% include local application site reactions (dry lips, desquamation, dryness of skin, cracked lips, burning skin, pruritus, flakiness of skin, and stinging on the skin) as per the package insert. Each event occurred in less than 1% of subjects receiving Zovirax® Cream 5%. Other adverse reactions (angioedema, anaphylaxis, contact dermatitis, eczema) as well as signs and symptoms of inflammation have been reported with Zovirax® Cream 5% use in clinical practice.

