6.5.4.3 Application Site Reaction Assessment

The application site reaction such as dry lips, desquamation, dryness of skin, cracked lips, burning skin, pruritus, flakiness of skin and stinging of the skin will be assessed as None, Mild, Moderate and Severe at Visit 2 (Day 1) and at each subsequent visit.

Application site reactions will not to be considered as adverse events unless they warrant temporary discontinuation of the study medication, discontinuation from the study or treatment with new concomitant medication.

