8.7.4 Other Observations Related to Safety

8.7.4.1 Physical Examination

The physical examination will be performed at Visit 1 (Screening) and Visit 2 (Day 1). A subject listing will be presented which will include:

- Whether physical examination was performed? (Yes/No)
- Examination date
- Were there any abnormal findings? (Yes/No)

8.7.4.2 *Vital Signs*

Vitals signs will be performed at Visit 1 (Screening) and Visit 2 (Day 1). [REDACTED]
[REDACTED]

[REDACTED]

[REDACTED]

8.7.4.3 *Application Site Reaction Assessment*

The severity (none, mild, moderate and severe) of application site reaction will be summarized by frequencies and percentages by visit.

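### SAP 8.7.4.3 tabulates scored application site reactions by scheduled visit only, so the visible plan gives no per-subject incidence or worst severity for reactions that lead to no action

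*SAP*

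**What the plan says.** **Collection.** Protocol 5.7.2 has eight reactions recorded from the first treatment day: "At Day 1 (Visit 2) and at each subsequent visit, application site reactions such as dry lips" and seven others, each scored none, mild, moderate or severe. Unscheduled visits are covered too. SAP 6.2.3 says "If a subject arrives on an unscheduled visit, then the same assessment procedures will be performed as a scheduled follow-up visit".

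**Which visits are summarized.** The same section then sets the rule "Data will be summarized as per scheduled study visits only", and it rules out reassigning other visits to scheduled ones by windowing. Its Table 3 lists Visits 2 to 13 and has no row for an End of Study visit.

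**The planned table.** Under SAP 8.7.4.3, the severity of "application site reaction will be summarized by frequencies and percentages by visit". No any-time or worst-severity row is mentioned, and no text in that section is blacked out.

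**Link to adverse events.** SAP 6.5.4.3 says "Application site reactions will not to be considered as adverse events unless they warrant temporary discontinuation of the study medication", or lead to withdrawal from the study or a new concomitant medication. Reactions that qualify are counted once per subject under SAP 8.7.2.

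**When subjects leave.** Protocol 3.3 keeps subjects who heal early in the study to Visit 6, which is then their End of Study visit. For later healing the rule reads "If the lesion is healed after Day 5 (Visit 6) but before Day 21 (Visit 13), the subject will return for their End of Study", after which attendance stops.

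**What the analysis is for.** Comparing the safety of test and reference is a study objective (Protocol 2, SAP 3). The protocol synopsis also undertakes to summarize the frequency and distribution of these eight reactions for the two active products, without naming the counting unit.

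**The concern.** Each rule is reasonable alone. Together they leave out the usual tolerability result, which is how many subjects in each arm had a given reaction at any time and how severe it became.

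These are the local reactions that Protocol 7 expects, and it reports the reference product's experience per subject: "Each event occurred in less than 1% of subjects receiving Zovirax". A by-visit table gives up to twelve separate percentages per reaction, and a reader cannot tell whether successive rows show the same few subjects or different ones. Two products could have matching by-visit rows and still differ in the number of subjects affected.

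The scheduled-visits rule also drops data that sites are told to collect. A subject who heals between visits is asked to come in promptly, and a reaction scored at that visit may fall outside every row of the table.

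**Working it through.** The documents state no site-reaction rate for this trial, so there is no planned figure to reproduce. The check has three parts.

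**1. Where a reaction with no consequence can appear.**
- Adverse event tables (SAP 8.7.2): no, by the 6.5.4.3 rule.
- By-visit table (SAP 8.7.4.3): yes if scored at a scheduled visit, no if scored only at another visit (6.2.3).
- Per-subject or worst-severity table: none is visible.
- Listings (SAP 7.1): yes, because all eCRF data are listed.

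**2. What by-visit rates say about incidence.** Assume a fraction p of the same group of subjects shows a reaction at each of k visits. The fraction ever affected is:
- smallest, p, if the same subjects are affected each time;
- largest, min(1, k × p), if no subject is affected twice;
- 1 − (1 − p)^k, if visits are independent.

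Take k = 5 (Visits 2 to 6), because nobody leaves on healing before Visit 6 and the group is then nearly constant. The values of p are assumptions.

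| p per visit | Same subjects | Independent | No overlap |
|---|---|---|---|
| 1% | 1.0% | 1 − 0.99^5 = 4.9% | 5 × 1% = 5.0% |
| 5% | 5.0% | 1 − 0.95^5 = 22.6% | 5 × 5% = 25.0% |

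The same five rows are thus compatible with a fivefold range in subjects affected. This holds even if every visit is on schedule.

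After Visit 6 healed subjects stop attending. SAP 8.7.4.3 does not say whether the by-visit denominator is subjects seen or, following SAP 8.7, all subjects dispensed medication. With the first, later rows describe slower healers only. With the second, absent subjects count as unaffected. Neither gives incidence.

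**3. Which visits are lost.** From Table 3, the scheduled days from Day 5 on are 5, 6, 7, 8, 10, 12, 13–15 and 19–23. That is 6 + 3 + 5 = 14 of the 19 days from Day 5 to Day 23. The other five (9, 11, 16, 17 and 18) lie outside every window. Days 1 to 8 are all scheduled.

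On the 14 in-window days a healing visit can coincide with a scheduled visit. Whether it is tabulated then depends on how the eCRF labels it. The visible text does not settle this: Protocol 3.3 treats Visit 6 as an End of Study visit, while SAP 6.5.3 names End of Study separately from Visit 13.

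**The case against.** The strongest objection is that the visit loss hardly touches exposure. Treatment lasts four days, Visits 2 to 6 are daily and scheduled, and early healers must attend through Visit 6. The first day outside Table 3 is Day 9, five days after the last treatment day. That is right, and it confines both the lost visits and the shrinking denominators to the post-treatment period.

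A reader might go further than the documents allow in four ways.

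- *End of Study visits are left out of the summaries.* Those that are scheduled visits, such as Visit 6, are counted. The documents give no healing distribution. If healing were lognormal with mean 5, 7 or 9 days (SD 3, 3.5, 4), simulation puts about 7%, 15% or 23% of End of Study visits on the off-window days, so most would fall on Table 3 days. An unhealed subject whose reaction persists is also counted at the next scheduled visit.
- *No per-subject incidence exists at all.* It does for reactions that prompt interruption, withdrawal or new medication (SAP 8.7.2).
- *Most reactions are barred from the adverse event tables.* The documents give no share.
- *Data are lost.* They are listed, though a listing does not summarize.

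It can also be said that a severity-by-visit table meets the synopsis wording, since no counting unit is promised, and that no planned analysis compares scored reactions with the label rates. Both are fair: the gap is in usefulness and is not a broken commitment. Finally, the visit schedules and the unscheduled and End of Study procedures are blacked out or not shown, and may say how such visits are labelled. They would not supply the missing per-subject table.

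**Conclusion.** The point holds as a reporting gap. For reactions that lead to no action, the visible plan has no per-subject incidence and no worst-severity summary, and the by-visit table cannot supply either. Under the assumed 1% at each of Visits 2 to 6, incidence could be 1% to 5%; at 5% per visit, 5% to 25%. These rates are illustrations, not forecasts.

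The off-schedule loss is a smaller, secondary matter. It affects transient reactions seen only on visits outside Table 3, mainly after treatment, and possibly End of Study records that are not mapped to a visit.

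SAP 8.7 draws no inference from safety data, so alpha, power and the equivalence and superiority conclusions are untouched. The change is still worth making, because comparing test and reference safety is an objective and the data are already collected.

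**What to change.** - Add one table to SAP 8.7.4.3, by treatment arm (all three). For each of the eight reactions and for any reaction, give the number and percentage of subjects by worst severity at any assessment after the first dose, whether scheduled, unscheduled or End of Study.
- Limit the scheduled-visits rule in SAP 6.2.3 to by-visit displays, and state how End of Study records map to visits.
- State the denominator. Dosed subjects with at least one post-dose assessment suit this table, but that departs from SAP 8.7, which bases safety percentages on everyone dispensed medication, including those who never dosed. Say so in the SAP, or show both.
- Keep the by-visit table for time course, and state its denominator.

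The cost is one more table from existing data, with no added visits or procedures. Reported percentages will generally be higher than the by-visit ones, which a footnote can explain.
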